3.5 Follow-up Visits - *up to Month 24*

Following the IMP implantation (Visit 3), 6 follow-up visits will be performed at the investigating site at Month 1, 3, 6, 12, 18 and 24.

However, if a treated patient is withdrawn/discontinued from the study any time before visit 9 at Month 24, he/she will no longer be asked to come for the remaining follow-up visits. In this case, an early discontinuation visit/Exit visit will be completed at the time of discontinuation and a follow-up visit will be performed at Month 24 (via phone call). The reason for withdrawal/discontinuation must be documented clinically and/or by the central radiologist if applicable.

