9 PREMATURE REMOVAL FROM THE STUDY

9.1 Reasons for Early Discontinuation

Notification of patient study discontinuation (and reasons for discontinuation) will be communicated by the Investigator as soon as possible. The Investigator will document the circumstances for premature discontinuation in the patient's electronic Case Report Form as follows:

- ***Violation of eligibility criteria***

Patients will be withdrawn if incorrectly randomised (*i.e.*, not in compliance with one or more eligibility criteria). The Investigator may contact the Monitor in order to discuss the potential continuation of wrongly included patients if judged that is in the interest of the patient to continue the study.

In any case, and especially if the patient is withdrawn for safety reasons, the explanation for this discontinuation due to violation of eligibility criteria should be documented in the patient's eCRF.

- ***Adverse Events / Serious Adverse Events***

Any patients may be withdrawn from the study at the Investigator's discretion in case of a safety concern. However, patients can be withdrawn from the study for AEs or SAEs **only** if the Investigator has clearly determined that the patient's withdrawal would reduce the safety risks. In this case, the eCRF AE/SAE Form must be completed, explaining the rationale for withdrawal. In addition, the Investigator should ensure that adequate medical care and management will be provided to the patient.

- ***Withdrawn consent***

Participation in the study is strictly voluntary. A patient has the right to withdraw his/her consent from the study at any time, and for any reason, without prejudice to further treatment, care, and patient-physician relationship. Under these circumstances, an adequate standard of care will always be adopted by the Investigator. The reason(s) for withdrawing consent will also be documented in source documentation and the eCRF.

- ***Lack of patient compliance to the protocol***

- ***Study termination***

The Sponsor has the right to terminate the study at any time.

PREOB-ON3 - Clinical Study Protocol

PREOB-ON3-CSP

V 6.1

Author: [name]

May 15, 2017

Pg. 82/83

- ***Lost to follow-up***

Intensive efforts will be made to re-contact patients who do not return for scheduled visits in order to, at minimum, determine health status and the potential occurrence of AE and/or SAE. All efforts to re-contact will be documented in the source documentation and the eCRF.

- ***Reaching of endpoint***

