Severe pain and/or femoral head fracture of the treated hip are the composites of the primary efficacy responder endpoint of this study. These events must carefully be documented either clinically for pain (WOMAC® VA 3.1) or radiologically for fracture (central radiologist assessment) before a patient is discontinued from the study. If severe enough to justify or warrant THA, these events will also be reported as SAE.

These events will be reported as study endpoints *via* the eCRF.

- ***Other reasons***

If no above-mentioned reasons are applicable in case of early discontinuation, the other reason(s) will be clearly documented and explained in the eCRF and source documents.

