9.2 Procedure for Early Discontinuation

In case of early discontinuation and whenever possible, Investigators will ask patients to perform Visit 9 (Exit Visit) as the Premature Discontinuation Visit. At the end of the Exit visit, the Investigator will declare early discontinuation in the eCRF. However, the Investigator will continue to follow the patient (via phone calls) for the occurrence of any AEs and SAEs at Month 24, 36 and 48 post-treatment (See Table 11).

All collected data, during the visits and phone calls, should be recorded in the source documents and eCRF.

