10.4 Sample Size

The single sample size test is planned with a two-sided 5% significance level and a power of 90% assuming the use of Chi-square test (see Table 14). The proportion of treatment responders

PREOB-ON3 - Clinical Study Protocol

PREOB-ON3-CSP V 6.1 Author: [name] May 15, 2017 Pg. 87/88

is assumed to be equal to 63% for the PREOB® group and 30% for the Placebo group. These hypotheses have been estimated on the basis of the Phase IIb data set.

Table 14: Sample size estimation - Chi-square test

Test?	Chi-square
Test significance level, α	0.05
1 or 2-sided test?	2
Group 1, PREOB® proportion, π_1	0.63
Group 2, Placebo proportion, π_2	0.30
Power (%)	90
N per arm	46

A Chi-square test with a 5% two-sided significance level will have 90% power to detect the difference between a Group 1 proportion, π_1 , of 0.63 and a Group 2 proportion, π_2 , of 0.30 when the overall sample size is 92 patients (46 patients in the PREOB® group and 46 patients in the Placebo group).

As an interim analysis is planned in the study using a group sequential design approach, the maximum sample size must be increased to achieve the desired power of 90% at final analysis. The increase in sample size depends on the overall significance level, the statistical power, the number of interim analyses and the type of boundaries being used (See section 10.7). Thus, the maximum sample size is obtained by multiplying the above fixed sample size by a constant determined by these parameters. For the current study, the maximum sample size is 110 patients (1.19 * 92 patients).

Taking into account a drop out and lost to follow-up rate of 7.5%, the overall sample size should be of 118 patients (59 patients in the PREOB® group and 59 patients in the Placebo group) to ensure around 110 evaluable patients at Month 24.

Sample size was computed using the procedure seqdesign of SAS® software version 9.2.

Additional considerations for sample size estimation

Although no claim is intended for the comparison of efficacy endpoints other than the primary endpoint, sample size calculations have been conducted to ensure that such comparisons may be performed with sufficient power to provide additional characterization of the treatment effect and yield supportive evidence related to the primary objective.

PREOB-ON3 - Clinical Study Protocol

PREOB-ON3-CSP

V 6.1

Author: [name]

May 15, 2017

Pg. 88/89

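### Month 24 pain score and X-ray are not scheduled for treated patients discontinued early, so the primary outcome of some of them is never observed

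*Combined protocol and SAP*

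**What the plan says.** Treatment is one implantation on Day 0 (protocol section 5.1). The primary endpoint in section 10.1.1 has two parts, both read at Month 24: a WOMAC VA3.1 pain improvement of at least 10 mm from baseline (or a score of 0 to 4 mm if baseline was below 10 mm), and no progression to ARCO III or higher on X-ray.

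Section 3.5 provides that a treated patient withdrawn or discontinued before Visit 9 "he/she will no longer be asked to come for the remaining follow-up visits". An exit visit takes place at discontinuation, and Month 24 becomes a phone contact. Section 9.2 adds that, whenever possible, "Investigators will ask patients to perform Visit 9 (Exit Visit) as the Premature Discontinuation Visit", and that the patient is then followed "via phone calls) for the occurrence of any AEs and SAEs at Month 24, 36 and 48 post-treatment". It names neither WOMAC nor X-ray for that call.

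The reasons in section 9.1 include "Reaching of endpoint", explained thus: "Severe pain and/or femoral head fracture of the treated hip are the composites of the primary efficacy responder endpoint". These events must be documented by WOMAC or by the central radiologist before the patient is discontinued. Other listed reasons are eligibility violation ("Patients will be withdrawn if incorrectly randomised", although continuation may be discussed with the Monitor), adverse events (only where withdrawal would reduce the safety risk) and lack of compliance.

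Section 10.6.1 analyses the primary endpoint after replacement of missing post-baseline data under rules placed in the SAP. Section 10.5 admits to the full analysis set any treated patient with baseline values and at least one post-baseline value of both measures. Section 10.4 allows for 7.5% loss.

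**The concern.** With a single implantation there is no continuing treatment to stop, so leaving the study gives no evident reason to stop measuring the outcome. Yet two of the events that can trigger discontinuation are themselves outcome events. The resulting gap in Month 24 data therefore depends on how the patient is doing.

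The pain wording adds a second difficulty. Section 9.1 treats severe pain as a component of the primary endpoint, with no threshold. Section 10.1.1 defines clinical response by change from baseline at Month 24. A patient discontinued for pain at Month 6 is not necessarily a Month 24 non-responder, and nobody will have looked.

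Part of the primary result would then come from a replacement rule where an observation could have been had. The WOMAC change scores at Month 24, and at visits skipped after exit, would also lose patients selected partly for doing badly. No rule written later can restore an assessment that was not made.

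**Working it through.** **1. The plan's own size.** Inputs from section 10.4: 63% v 30%, two-sided 5%, 90% power. Mean rate (0.63 + 0.30)/2 = 0.465.

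n per arm = [1.960·√(2·0.465·0.535) + 1.282·√(0.63·0.37 + 0.30·0.70)]² / 0.33² = 45.9, so 46, as stated. Then 1.19 × 92 = 109.5, so 110 (the factor 1.19 is taken as given), and 118 × 0.925 = 109.2, which matches the stated target of around 110 evaluable patients. The allowance is 118 × 0.075 = 8.85, about 9 patients.

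**2. What is known at Month 24, by reason for discontinuation.**

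| Reason (9.1) | Month 24 WOMAC and X-ray scheduled? | Can status be settled without them? |
|---|---|---|
| Fracture, centrally documented | No | Yes: the radiological component has failed, barring reversion |
| Severe pain alone | No | No: pain may change, and severe is not defined |
| Eligibility violation | No | No |
| Non-compliance | No | No |
| Adverse event | No | No, unless fracture is also documented |

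**3. How many could be affected.** The documents give no discontinuation rates, so the share of failures discontinued is an assumption. Planned failure rates are 1 − 0.63 = 37% and 1 − 0.30 = 70%. Patients without a Month 24 assessment = share × failure rate × 59.

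| Share of failures discontinued | PREOB | Placebo | Of 118 |
|---|---|---|---|
| One quarter | 0.25 × 0.37 × 59 = 5.46 | 0.25 × 0.70 × 59 = 10.33 | 15.8 (13%) |
| One half | 10.9 | 20.6 | 31.6 (27%) |
| All | 21.8 | 41.3 | 63.1 (54%) |

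These counts include fracture cases, which can be classified, so the unresolvable part is smaller. They exclude ineligible, non-compliant and adverse-event discontinuations among patients who would have responded. The documents allow no further split.

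**4. What the analysis rule does to the contrast.** If every discontinued failure counts as a non-responder, the rates stay at 63% v 30%. With 59 per arm at the final level in section 10.7 (0.01341 per tail, 0.02682 two-sided), fixed-sample power, ignoring the interim look, is

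Φ{[0.33·√59 − 2.214·√(2·0.465·0.535)] / √(0.63·0.37 + 0.30·0.70)} = Φ(1.46) = 92.8%.

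If 7.5% of each arm left regardless of outcome and were counted as non-responders, the rates would be 0.63 × 0.925 = 58.3% and 0.30 × 0.925 = 27.8%, a difference of 30.5 points.

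Exclusion is not what section 10.6.1 plans. For comparison, excluding a quarter of the failures gives 0.63/(1 − 0.0925) = 69.4% v 0.30/(1 − 0.175) = 36.4%, a difference of 33.1 points. Excluding half gives 0.63/0.815 = 77.3% v 0.30/0.65 = 46.2%, a difference of 31.1 points. The contrast hardly moves at low discontinuation and shrinks as it rises.

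**The case against.** The strongest reply is that little is really lost. Discontinuation is permitted, not required: ineligible patients may stay after discussion, withdrawal for adverse events is restricted, and no sentence says that every patient with severe pain or fracture must leave. Pain or fracture must be documented first, an exit visit is requested, and calls follow at Months 24, 36 and 48. Many failures can therefore be classified, and a replacement rule is promised. All of this stands, and it limits the size of the problem. It does not supply a Month 24 pain score or X-ray for patients who leave for pain alone or for reasons unrelated to fracture.

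Three stronger readings are tempting, and the documents do not support them.

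- A reader might infer a large loss of power, by applying the Phase IIb two-year fracture rates of 20% and 40% (section 1.1.3.2) and dropping those patients. Section 10.6.1 plans replacement, not exclusion; fractures are the very cases that can be settled; and the 40% comes from an active comparator, bone marrow concentrate.
- A reader might infer that the loss falls more on placebo. No section gives rates by arm. The imbalance in the illustration only mirrors the planned failure rates and would not arise if the arms did not differ.
- A reader might infer that early exits will be analysed as Month 24 data because they are performed as Visit 9. Section 3.5 places the exit visit at the time of discontinuation, so the natural reading is that Visit 9 procedures are brought forward. The text simply does not exclude the other use.

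**Conclusion.** The point holds in limited form. Under sections 3.5 and 9.2 the Month 24 measurements that define the primary endpoint are not scheduled for treated patients discontinued early, and some listed reasons for discontinuation are outcome events. Documented fractures are not the difficulty. The gap is patients discontinued for pain alone, ineligibility, non-compliance or adverse events, whose Month 24 status would rest on replacement rules that are not in the text reviewed.

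The size cannot be established from the documents. The 13% figure assumes that the planned response rates hold and that a quarter of failures are discontinued. It exceeds the 7.5% allowance, but a documented failure may still be evaluable, so it does not show that the target of around 110 evaluable patients is missed. Neither a direction of bias nor a power deficit is demonstrated. The case for change is that the loss is avoidable, depends partly on outcome, and cannot be undone at database lock.

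**What to change.** Amend sections 3.5, 9.1 and 9.2 as follows.

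- Record discontinuation and its reason, but continue to ask treated patients for the scheduled efficacy assessments, at minimum Month 24 WOMAC VA3.1 pain and X-ray. Exceptions are withdrawal of consent to follow-up and imaging precluded by pregnancy under section 8.4.
- For patients who decline site visits, use the Month 24 call already planned to obtain arthroplasty status and a phone WOMAC, as supportive data only.
- Enter early exit visits under their actual date and do not analyse them as Month 24 observations.
- Reconcile the severe-pain wording in section 9.1 with the response definition in section 10.1.1, and state how each reason for discontinuation is classified in the primary analysis.

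The cost is an amendment and a few additional visits for patients who have already failed or left the study. The sample size need not rise.

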3.5.1 Follow-up Visit 4 [REDACTED] and Visit 5 [REDACTED]

Patients will be evaluated as follows:

[REDACTED]

[REDACTED]

PREOB-ON3 - Clinical Study Protocol

PREOB-ON3-CSP

V 6.1

Author: [name]

May 15, 2017

Pg. 51/52

3.5.2 Follow-up Visit 6 and Visit 7

Patients will be evaluated as follows:

3.5.3 Follow-up Visit 8

Patients will be evaluated as follows:

PREOB-ON3 - Clinical Study Protocol

PREOB-ON3-CSP

V 6.1

Author: [name]

May 15, 2017

Pg. 52/53

3.5.4 Follow-up Visit

Patients will be evaluated as follows:

Term	Percentage
GDP	85
Inflation	85
Interest rates	90
Central bank	90
Monetary policy	85
Quantitative easing	80
Institutional investors	75
Fintech	70
Algorithmic trading	65
Blockchain	60
Smart contracts	55
RegTech	50
FinTech	45
Regulatory沙盒	40

End-of-period examination: This 24-month visit corresponds to the end of study examinations at the Investigating Site.

3.6 Long Term Follow-up (Months 36 and 48 [REDACTED])

For all treated patients (*i.e.*, even for patients who have been withdrawn/discontinued from the study before the end of the 24-month follow-up period), phone call “visits” will be performed by the Investigator at 36 months [REDACTED] (Visit 10) and 48 months [REDACTED] (Visit 11) after IMP implantation, to evaluate the following safety data:

- Assessment of any changes in health status
- Review of concomitant medication
- Documentation of SAE (notably in case of THA)

**PREOB-ON3 - Clinical Study Protocol**

PREOB-ON3-CSP

V 6.1

Author: [name]

May 15, 2017

Pg. 53/54

Patients who have completed all the follow-up visits (*i.e.* up to Month 24 included) will also be evaluated for the following clinical variables:

[REDACTED]

[REDACTED]

[REDACTED]

[REDACTED]

[REDACTED]

PREOB-ON3 - Clinical Study Protocol

PREOB-ON3-CSP

V 6.1

Author: [name]

May 15, 2017

Pg. 54/55

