2.2.2 Long Term Follow-up

A long-term follow-up will be performed via phone calls at 36 and 48 months after IMP implantation. This includes assessment of hip symptoms (pain, stiffness, and function) using WOMAC® LK3.1 (Likert Scale), radiological progression (conventional X-ray to be performed only when the patient still feels pain on the treated hip), and the potential occurrence of any AEs and SAEs (patient open questionnaire, including notably any changes in health status and need for total hip arthroplasty).

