2.2.3 Clinical Study Report

The Final Clinical Study Report will be established based on the efficacy and safety data collected up to Month 24. The long-term follow-up data will be analysed and reported as Annexes and Supplementary Data to the Final Clinical Study Report.

PREOB-ON3 - Clinical Study Protocol

PREOB-ON3-CSP	V 6.1	Author: [name]	May 15, 2017	Pg. 36/37
---------------	-------	----------------	--------------	-----------

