2.3.4 Blinding

The study will be conducted double-blind with reference to the evaluation of trial results.

Briefly:

- The only physician to know patient group assignment is the Independent Physician, performing the (sham) bone marrow harvesting procedure.
- Investigators and Patients are blind to treatment assignment. Both patient groups undergo a bone marrow harvest, real or sham, performed by the Independent Physician, and a Core decompression/Implantation procedure performed by the Investigator, following identical procedures.
- The Investigational Medicinal Product, PREOB® and Placebo, are supplied in identical packaging conditions. The final product is packaged in a blind ready to use syringe.
- Radiologists are blind to the group assignment. All images (conventional X-ray, MRI and CT) will be processed to ensure blinding, notably coding and masking of posterior iliac crest through a Centralized Medical Imaging System. Processed images (*i.e.* blind) will be analysed by a single reader (Central Radiologist).
- To ensure the blinding of the study, imaging data should not be distributed to the patient and/or to the blinded study staff. However, if distribution is required (for any reasons), the imaging data should be masked at the harvesting region (iliac crest) prior to distribution, or depending on local Hospital policy.
- Blinding will only be lifted after completion of all study visits from all patients.

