2.4 Long -Term Follow-up

A long-term follow-up will be performed via phone calls at 36 and 48 months after IMP implantation. This includes assessment of hip symptoms (pain, stiffness, and function) using WOMAC® LK3.1 (Likert Scale), radiological progression (conventional X-ray to be performed only when the patient still feels pain on the treated hip) and the potential occurrence of any AEs and SAEs (patient open questionnaire, including notably any changes in health status and need for total hip arthroplasty).

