8.2.1 Observation period for the occurrence of AEs and SAEs

Table 11 below defines the observation period for the occurrence of AE and SAE during both the follow-up period (up to 24 months) and the long term follow-up (at 36 and 48 months). These safety observation periods must be respected for all treated patients (*i.e.*, regardless of the patient's outcome in the study, whether the patient has been withdrawn/discontinued early or not).

Table 11: Observation period for the occurrence of AEs and SAEs

Follow-up: AE/SAE Observation Period	From Screening Period up to 24 months after implantation (Visit 3)
Long term follow-up: AE/ SAE Observation Period	At 36 and 48 months after implantation (Visit 3)

If the investigator learns of any SAE, including a death, any time after the two defined observation period for the occurrence of AEs and SAEs (Table 11), and considers the event reasonably related to the Investigational Medicinal Product, the investigator will promptly notify the Study contact for reporting SAEs.

PREOB-ON3 - Clinical Study Protocol

PREOB-ON3-CSP

V 6.1

Author: [name]

May 15, 2017

Pg. 72/73

8.2.2 *Summary of Possible Risks related to the Procedures*
Table 12: Summary of Possible Risks related to the Procedures

	AE	SAE (Fatal and Non-Fatal)
Bone Marrow Harvest	Pain at the aspiration site Local haematoma	-
Bone Marrow Concentrate/Mesenchymal Stromal Cells Implantation	Fever	-
Core Decompression and Implantation Procedure	Surgery Pain at the implantation site Local haematoma Infectious complications General anaesthesia Transient hypotension Nausea and vomiting	Surgery Femoral neck fracture Femoral head blow-up Haemorrhage Sepsis Shock General anaesthesia Cardiac complications 
 • Myocardial infarction • Cardiopulmonary arrest • Ventricular tachycardia Neurological complications 
 • Stroke Pulmonary complications 
 • Inhalation pneumonia • Pulmonary embolism Anaphylactic shock
Blood Sampling	Pain at the sampling site Local haematoma Superficial vein thrombosis Transient hypotension/lypothermia	Syncope

PREOB-ON3 - Clinical Study Protocol

PREOB-ON3-CSP | V 6.1 | Author: [name] | May 15, 2017 | Pg. 73/74

8.2.3 Summary of Observed Adverse Events (AE) and Serious Adverse Events (SAE) possibly related to Study Treatment in Osteonecrosis

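### Month 36 and 48 clinical data are limited to Month 24 completers, and X-rays to painful hips, so the long-term efficacy data can be selected by outcome

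*Combined protocol and SAP*

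**What the plan says.** Section 3.6 sets up two tiers of telephone follow-up at Months 36 and 48.

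- **Safety tier.** It covers all treated patients, "even for patients who have been withdrawn/discontinued from the study before the end of the 24-month follow-up period". The items are changes in health status, concomitant medication and "Documentation of SAE (notably in case of THA").
- **Clinical tier.** It covers only "Patients who have completed all the follow-up visits", Month 24 included. The list of clinical variables is redacted.

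Sections 2.2.2 and 2.4 name the long-term assessments: hip symptoms on WOMAC LK3.1, and "radiological progression (conventional X-ray to be performed only when the patient still feels pain on the treated hip"). Neither section restricts them to completers.

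Section 9.1 includes reaching the endpoint among the reasons for early discontinuation, and names severe pain and femoral head fracture of the treated hip. Under Sections 3.5 and 9.2 site visits then stop. After an exit visit, the patient is telephoned for AEs and SAEs at Months 24, 36 and 48.

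On reporting, Section 2.2.3 states: "The Final Clinical Study Report will be established based on the efficacy and safety data collected up to Month 24". The long-term data follow as annexes and supplementary data.

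**The concern.** Completing all visits to Month 24 is itself affected by outcome. A patient whose hip fractures or becomes severely painful may be discontinued, and then leaves the clinical tier although the investigator still telephones. The patients left for a Month 36 or 48 symptom comparison are no longer the randomised groups. They are those who did well enough to stay, and that filter need not act equally in the two arms.

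The X-ray rule adds a second filter. Pain is a component of the primary endpoint, and here it decides whether progression is looked for at all. A pain-free hip without an X-ray is unobserved, not progression-free. Section 10 gives no analysis set for Months 36 and 48 and no rule for hips without an X-ray.

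At stake is whether the long-term symptom and progression results, which will be analysed and reported, can be read as a comparison of treatments.

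**Working it through.** **Check on inputs.** The protocol gives no figure for the Month 36/48 comparison, so the only stated figure to reproduce is the Month 24 sample size (Section 10.4). With p1 = 0.63, p2 = 0.30, two-sided 5% and 90% power, the pooled-variance formula is

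n = [1.960 × √(2 × 0.465 × 0.535) + 1.282 × √(0.63 × 0.37 + 0.30 × 0.70)]² / 0.33² = 46 per arm, as stated.

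Then 1.19 × 92 = 109.5, rounded to 110. And 110 / 0.925 = 118.9, against 118 stated (118 × 0.925 = 109.2, in line with the stated aim of around 110).

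**Illustration 1: Month 24 failures discontinue.** Let p be the Month 24 responder rate and f the share of failures discontinued before Month 24. The documents give no f, so the whole range is shown. I assume 59 treated per arm, no other losses, and the same f in both arms. The fraction completing is c = p + (1 − p)(1 − f), and the responder rate among completers is p / c.

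| f | Assessable, PREOB v placebo | Month 24 responders among them | Difference (points) |
|---|---|---|---|
| 0 | 59 v 59 | 63.0% v 30.0% | 33.0 |
| 0.25 | 53.5 v 48.7 | 69.4% v 36.4% | 33.1 |
| 0.50 | 48.1 v 38.3 | 77.3% v 46.2% | 31.1 |
| 0.75 | 42.6 v 28.0 | 87.2% v 63.2% | 24.0 |
| 1 | 37.2 v 17.7 | 100% v 100% | 0 |

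If f differs by arm, the direction is open. With f = 0.5 in the PREOB arm only, the difference is 77.3 − 30.0 = 47.3 points. With f = 0.5 in the placebo arm only, it is 63.0 − 46.2 = 16.8 points.

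**Illustration 2: only fractured hips discontinue.** Section 1.1.3.2 gives Phase IIb two-year fracture rates q of 20% and 40%. These are rates for hips, and the comparator was bone marrow concentrate. The number assessable is 59 × (1 − q × f), and the fracture rate among them is q(1 − f) / (1 − q × f).

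| f | Assessable | Fractured by Month 24 among them |
|---|---|---|
| 0 | 59 v 59 | 20% v 40% |
| 0.50 | 53.1 v 47.2 | 11.1% v 25.0% |
| 1 | 47.2 v 35.4 | 0% v 0% |

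**X-ray rule.** In Phase IIb, treatment response required both pain relief and no fracture. Pain responders minus treatment responders therefore gives hips with relief that had fractured: 76.7 − 70.0 = 6.7% and 50.0 − 36.7 = 13.3%. As shares of fractured hips these are 6.7/20 and 13.3/40, about one third in each arm. Fractured hips without relief are 20 − 6.7 = 13.3% and 40 − 13.3 = 26.7%. If X-rays were taken only in hips without relief, the detected ratio would be 13.3/26.7 = 0.50, the same as the true 20/40 = 0.50. The risk difference would shrink from 20 to 13.4 points. Relief of 10 mm is not absence of pain, so one third is a rough upper guide to the fractures missed.

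**The case against.** The case against giving this weight is substantial.

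- **Status.** Every listed primary and secondary endpoint ends at Month 24, the synopsis puts long-term follow-up under safety, and Section 10.4 intends no claim beyond the primary endpoint. This stands: there is no planned long-term test to protect.
- **Redaction.** That WOMAC and X-ray are the restricted items is inferred from Sections 2.2.2 and 2.4. This also stands, but the completer restriction itself is in clear text, and those two sections do not repeat it.
- **Discontinuation is not mandatory.** Section 9.1 requires pain or fracture to be documented before a patient is discontinued; it does not say that every such patient must be. A fracture first seen at the Month 24 visit belongs to a completer. So f could be small.
- **Progressed hips tend to hurt.** Section 1.2 describes severe, continuous pain in advanced stages, so a pain trigger should find many progressions.
- **Arthroplasty is covered.** It is already sought in all treated patients. This stands, and the fix relies on it.

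Two further readings might be inferred and are not supported. One is that non-serious AEs are dropped because Section 3.6 names only SAEs. That section also asks about changes in health status, which Section 8.2 uses to elicit AEs, and Table 11 covers both, "At 36 and 48 months after implantation (Visit 3"). The other is that late scores are open-label because the report is built on Month 24 data. Section 2.3.4 says "Blinding will only be lifted after completion of all study visits from all patients", the calls are numbered Visits 10 and 11, and nothing says patients or investigators are unblinded earlier. Both are points of wording.

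**Conclusion.** The point holds in a limited form. Followed as written, Sections 3.6 and 9.1 can condition the long-term symptom data on Month 24 outcome, and the X-ray rule leaves progression unobserved in pain-free hips. The Month 24 primary result is untouched. Because the data will be reported, a cheap correction should be made.

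Neither size nor direction can be fixed from the documents. With equal f, the responder difference among completers lies anywhere from about 33 points to 0. With fracture-only discontinuation, assessable numbers lie between 59 v 59 and 47 v 35. These ranges rest on the planned or Phase IIb rates, 59 treated per arm and no other losses. The 47 v 35 end requires every fractured hip to be discontinued and is a limit, not a forecast.

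A reader might go further and conclude that the X-ray rule creates a benefit from nothing. For example, multiplying Phase IIb non-relief (23.3% v 50.0%) by an equal 20% progression gives 4.7% v 10.0%, a ratio of 0.47. That needs pain and progression to be independent. The Phase IIb figures contradict this: about two thirds of fractured hips lacked relief in both arms, and on that pattern the ratio is not distorted. Nor can one say that completer selection favours PREOB: with equal f it mostly dilutes the difference.

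**What to change.** 1. In the calls already made, ask WOMAC LK3.1 of every treated patient, and make Section 3.6 agree with Sections 2.2.2 and 2.4. Section 1.2 notes that this version is validated for telephone use.
2. In any long-term responder summary, count documented fracture or arthroplasty of the study hip as failure, and do not score a replaced hip as improved. The pain criterion needs its own definition on the Likert scale, because the 10 mm rule belongs to WOMAC VA3.1.
3. Use arthroplasty of the study hip, in all treated patients, as the between-arm long-term structural outcome.
4. Report progression found on pain-triggered X-rays as a descriptive listing, with the number of hips X-rayed per arm, and make no between-arm comparison.
5. Wording: align Section 3.6 with Table 11 on AEs and SAEs, and state that patients, investigators and callers stay blind until the last Month 48 call.

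The cost is a few more minutes per call for non-completers, plus amendment and SAP wording. No new visits or imaging are needed.
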